7.2.7 End of Study

For the entire study, end of study is defined as the last subject visit.

8 PROCEDURES AND VARIABLES

8.1 Population Characteristics

8.1.1 Demographic and Other Baseline Characteristics

Up to 12 subjects aged \geq 18 years, with confirmed CRC with confirmed liver metastases will be included.

8.1.2 Medical and Surgical History

Relevant medical and surgical histories are to be recorded for the following body systems: head, ear, eye, nose, throat, respiratory, cardiovascular, gastrointestinal, genitourinary, musculoskeletal, endocrine, neurological, psychiatric, and skin/dermatological.

As part of the medical history, the date of the last spontaneous menstruation will be recorded, if childbearing potential is not excluded by surgical sterilization.

8.1.3 Prior and Concomitant Medication

All medications taken 30 days prior to injection through the 5 ± 3 day follow-up visit will be documented.

8.2 Safety

8.2.1 Adverse Events

8.2.1.1 Definition of Adverse Event

The definitions below follow International Conference on Harmonization (ICH) – Good Clinical Practice (GCP) (see also ICH Guideline for Clinical Safety Data Management: Definitions and Standards for Expedited Reporting).

Adverse Event (AE)

An AE is defined as any untoward medical occurrence in a subject administered a pharmaceutical product and which does not necessarily have a causal relationship with this treatment. An AE can therefore be any unfavorable and unintended sign (including an abnormal laboratory finding), symptom, or disease temporally associated with the use of a medicinal (investigational) product, whether or not considered related to the medicinal (investigational) product.

By definition for this trial, all untoward medical occurrences beginning on the day of injection through the assessment 5 days post-injection are to be reported as AEs. Additionally, untoward medical events occurring prior to the day of injection and after the 5 ± 3 day post-injection follow-up will only be captured as AEs if they are related to a trial procedure or study drug. Any clinically significant change in condition (worsening) from screening that results in a change in subject management will be considered an AE and will be recorded on the AE page of the CRF. SAEs will be reported from the time of consent through the end of participation.

8.2.1.2 Categories for Adverse Event Assessment

All AEs will be assessed and documented by the investigator according to the categories detailed below

Severity

The severity of an AE is classified according to the following categories, taking into account the possible range of the intensity of the event:

- **Mild** The AE is transient and easily tolerated by the subject.
- **Moderate** The AE causes the subject discomfort and interrupts the subject's usual activities
- **Severe** The AE causes considerable interference with the subject's usual activities and may be incapacitating or life-threatening.

Specific drug treatment

Any specific drug treatment will be documented.

Causal relationship to investigational product

The investigator will use the following definitions to assess the relationship of the AE to the use of IP:

Definitely related: Event can be fully explained by administration of the IP.

Probably related: Event is most likely to be explained by administration of the IP rather than the subject's clinical state or other agents/therapies.

Possibly related: Event may be explained by administration of the IP or by the subject's clinical state or other agents/therapies.

Probably not related: Event is most likely to be explained by the subject's clinical state or other agents/therapies, rather than the IP.

Definitely not related: Event can be fully explained by the subject's clinical state or other agents/therapies.

For causality assessments, events meeting the categories of definitely, probably, or possibly related will be considered to be related to IP.

Outcome

The outcome of the AE is to be documented as follows:

- **Resolved**
- **Resolved with sequelae**
- **Ongoing**

- Unknown
- Lost to follow-up
- Death

8.2.1.3 Assessments and Documentation of Adverse Events

Attention shall be paid to the occurrence of AEs at all stages of the SPECT evaluation. Thus, the subject should be closely observed by the investigator both during and after the evaluation.

Any AE (observed, volunteered, or elicited) should be recorded in detail in the source documentation.

The following information is required:

- The **date and time of onset** of any AE.
- The **duration** (the entire duration of an event or symptom, calculated from date of onset to date of end, if not recorded directly).
- The **seriousness** of the AE will be assessed by the investigator. If the investigator deems that an AE qualifies as an SAE, a special form provided by the sponsor should be completed and the event must be immediately reported to the sponsor. A definition of SAEs is provided below.
- The maximum **intensity** (mild, moderate, or severe).
- Specific drug treatment
- The **relationship** of the AE to the IP and to trial conduct (for definitions, see above).
- The **outcome** of the AE (resolved, resolved with sequelae, ongoing, unknown, lost to follow-up, death).

AEs will be coded according to an internationally recognized dictionary (Medical Dictionary for Regulatory Activities [MedDRA]).

8.2.1.4 Expected Adverse Events

Expected Adverse Drug Reactions

The definition below follows ICH-GCP (see also ICH Guideline for Clinical Safety Data Management: Definitions and Standards for Expedited Reporting):

Adverse Drug Reaction (ADR)

In the pre-approval clinical experience with a new medicinal product or its new usages, particularly as the therapeutic dose(s) may not be established, all noxious and unintended responses to a medicinal product related to any dose should be considered as adverse drug reaction (ADR). The phrase 'responses to a medicinal product' means that a causal relationship between a medicinal product and an AE is at least a reasonable possibility (definitely, probably, possibly), i.e., the relationship cannot be ruled out.

Investigational Product-Related Risks

In previous clinical trials with tilmanocept (n = 553 subjects injected subcutaneously, intradermally, subaereolarly, peritumorally), all individual AEs were experienced by less than \leq 1% of all subjects enrolled in sponsor-initiated trials. The most commonly reported AEs in all subjects were injection site irritation, which occurred in 0.6% (n = 3), and pain, which occurred in 0.2% (n = 1) of all subjects. All other treatment-emergent AEs occurred in 0.2% or less of all subjects. AEs from the radioactive dose are not expected, since the applied radiation doses are far below doses that can cause acute effects in human tissues.

Precautionary Measures

Special precautionary measures are not considered to be necessary for this trial. In case of emergency, standard emergency procedures will be employed.

Unexpected Adverse Drug Reactions

An unexpected ADR is defined as an adverse reaction that in nature and severity is not consistent with the applicable product information (e.g., Investigator's Brochure [IB]).

Any adverse experience that is not listed in the current IB or which is, with regard to the specificity or severity, not consistent with the risk information shall be regarded as unexpected.

Hypothetical examples would be (a) acute renal failure listed in the IB with a subsequent new report of interstitial nephritis and (b) hepatitis with a first report of fulminant hepatitis. "Unexpected" as used in this definition refers to an adverse drug experience that has not been previously observed and included in the product information, rather than from the perspective of such experience not being anticipated from the pharmacological properties of the IP.

8.2.1.5 Serious Adverse Events

Definition of Serious Adverse Events

The following SAE definition is based on ICH guidelines and the final rule issued by the FDA and effective 06 Apr 1998.

An SAE is classified as any untoward medical occurrence that at any dose:

- results in death, or
- is life threatening, or
- requires inpatient hospitalization or prolongation of existing hospitalization, or
- results in persistent or significant disability/incapacity, or
- is a congenital anomaly/birth defect, or
- is an important medical event (see paragraphs below).

The term 'life threatening' in the definition refers to an event in which the subject was at risk of death at the time of the event; it does not refer to an event that hypothetically might have caused death if it were more severe.

Medical and scientific judgment should be exercised in deciding whether it is appropriate to report an AE as serious also in other situations, such as important medical events that may not be immediately life threatening or result in death or hospitalization but may jeopardize the subject or may require intervention to prevent one of the other outcomes listed in the definition above. These should also usually be considered serious. Examples of such events are intensive treatment in an emergency room or at home for allergic bronchospasm or blood dyscrasias or convulsions that do not result in subject hospitalization.

Actions and reporting obligations in case of SAEs

The investigator should take appropriate diagnostic and therapeutic measures to minimize the risk to the subject.

If any SAE occurs over the course of the trial, investigators or other site personnel will inform Navidea Biopharmaceutical representatives within one day (i.e., within 24 hours) of becoming aware of the SAE. Written notification on FRM-1084 of the SAE will be emailed to Navidea Biopharmaceuticals Pharmacovigilance at [contact].

For fatal or life-threatening adverse events where important or relevant information is missing, active follow-up is undertaken immediately.

All SAEs must also be recorded on the AE CRFs.

Notification of the IRB(s)

The sponsor and/or the investigator will notify the IRB(s) about all relevant events (e.g., SAEs and suspected, unexpected, serious adverse reactions [SUSARs]) according to all applicable regulations.

Notification of the authorities

The sponsor will process and report all relevant events (e.g., SAEs, SUSARs) to the authorities according to all applicable regulations.

Sponsor's notification of the investigators

The sponsor will inform the investigator about reported relevant events (e.g., SAEs, SUSARs) according to all applicable regulations.

8.2.2 Further Safety Assessments

8.2.2.1 Physical Examination

Physical examinations will be performed for the following body systems:

- General appearance
- Skin/dermatological
- Eyes, ears, nose, throat
- Head and neck (including thyroid)
- Lungs

- Heart
- Abdomen (liver, kidney, spleen, gastrointestinal)
- Lymph nodes
- Musculoskeletal

8.2.2.2 Vital Signs

Vital signs comprise the measurement of body temperature, heart rate, systolic and diastolic blood pressure, and respiratory rate. All measurements will be taken after the subject has been in a resting position for at least 5 minutes. Measurements will be taken at Screening, Day 1 predose (15 minutes before injection), and postdose (within 15 minutes after injection).

Any clinically significant change from screening (worsening) that results in a change in subject management will be considered an AE and will be recorded on the AE page of the CRF.

8.3 Other Procedures and Variables

8.3.1 Clinical Laboratory Parameters for Screening and Safety

Clinical laboratory tests to be evaluated in this trial include hematology, serum chemistry and urinalysis. Blood and urine samples for safety will be obtained at screening.

Subjects will be in a seated or supine position during blood collection. Clinical laboratory tests will include the following:

Table 3. Clinical Laboratory Parameters

Hematology	hemoglobin (Hgb), platelets, white blood cell (WBC)
Serum chemistry	creatinine, chloride, potassium, sodium, carbon dioxide /bicarbonate, blood urea nitrogen (BUN), alanine aminotransferase (ALT), aspartate aminotransferase (AST)
Urinalysis	pH, specific gravity

The investigator will provide a list of normal ranges of the local laboratory prior to the start of the study. The University of Alabama Birhmingham laboratory will provide the necessary supplies to collect the blood and urine samples.

All laboratory reports must be promptly reviewed by the investigator, and upon review, initialed and dated by the investigator. Change(s) in postdose test values considered clinically significant, which would require either additional control or therapy, must be specified in the source documentation and, in case of disturbing or influencing factor(s) on values/samples, details of the appropriate value(s) and the source of disturbance or influence (e.g., quality of sample, co-medication) are to be recorded. GCP would suggest that a copy of the laboratory results also be provided to the subject's referring physician.

Any change in laboratory value which results in a change in subject management (additional controls or treatment required) will be reported as a clinically significant change. Clinically significant changes in laboratory parameters which are not the result of laboratory error are to be recorded as AEs.

Any clinically significant changes in laboratory values are to be followed up with repeated tests at appropriate intervals (as determined by the investigator and the Medical Monitor) until the values return to baseline level or until the abnormality is explained by the investigator.

8.3.2 Blood Sampling

The total amount of blood withdrawn during the trial will be approximately 20 mL over a period of approximately 2 weeks as shown in Table 4.

Table 4. Amount of Blood Withdrawn

Time point of examination	Amount of blood taken
Laboratory examination (Screening)	10 mL
Follow-up	10 mL
Total	20 mL

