2 TRIAL OBJECTIVES

2.1 Primary Objective(s)

- Estimation of the concordance of Tc99m localization in liver metastases from colorectal carcinoma (CRC) using SPECT/CT imaging and abdominal FDG PET/CT imaging per subject.
- Evaluation of safety including monitoring the incidence of adverse events and changes over time in laboratory tests, vital signs, and physical examination findings.

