4.2 Exclusion Criteria

Subjects who meet any of the following criteria will be excluded from the study.

1. The subject is pregnant or lactating;
2. The subject has undergone any liver surgery, exclusive of a biopsy;
3. The subject has known sensitivity to dextran;
4. The subject has had preoperative chemotherapy, immunotherapy, or radiation therapy within the 10 days prior to Tc 99m Tilmanocept administration;
5. Before the administration of Tc 99m Tilmanocept, has received any radiopharmaceutical within 7 radioactive half-lives of that radiopharmaceutical;
6. Has received an investigational product within the 30 days prior to Tc 99m Tilmanocept administration

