7 STUDY PROCEDURES

7.1 Screening Visit (Day -29 to Day 0)

- Obtain signed informed consent for study participation
- Preliminary review of inclusion and exclusion criteria
- Allocation of unique subject number; this number will be used to document the subject data in the case report form (CRF) and enrollment log
- Interview including the following subject-specific characteristics:
 - Demographic data
 - Medical/surgical history (including concomitant diseases)
 - Medication history
- Vital signs (body temperature, heart rate, blood pressure, and respiratory rate).
- Blood draw for routine hematology and chemistry
- Urine collection for routine urinalysis and for pregnancy testing for women of child-bearing potential. Females of child bearing potential are defined as women that are not surgically sterile (hysterectomy or bilateral oophorectomy) nor postmenopausal for at least 1 year prior to screening. Women who are not of childbearing potential will not require a pregnancy test.
- Physical examination including height and weight and a review of major body systems; any clinically relevant finding is to be documented as baseline finding.
- Subjects will undergo a FDG PET/CT scan to identify hepatic lesions.

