7.2 Day 1 (Injection and Imaging Procedures)

7.2.1 Before Injection

- Assessment of AEs
- Concomitant medication review
- Final check of inclusion/exclusion criteria
- Vital signs (body temperature, heart rate, blood pressure, and respiratory rate) within 15 minutes

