Appendix 1 Schedule of Events

Evaluation	VISIT 1 Screening Days -29 to 0	VISIT 2 Injection and Imaging Procedures Day 1		VISIT 3 Follow-up Day 5±3
		0:00	4-6 hrs	
Informed Consent	x			
Entry Criteria	x			
Medical History	x			
Vital Sign Assessment	x	x ^{bd}	x	x
Physical Examination	x ^c			x
Review of Medications	x	x		x
Clinical Laboratory Evaluation	x			x
Urine Pregnancy Test	x	x ^a		
Tc99m tilmanocept Administration		x		
FDG PET/CT Imaging	x			
SPECT/CT Imaging			x	
Adverse event Monitoring	x	x	x	x

- a. Urine dipstick pregnancy test must be completed and determined to be negative in women of childbearing potential within 48 hours of injection.
- b. Time point 0:00 is before tilmanocept injection (a 15 minute pre-injection window is permitted).
- c. Physical examinations done within 30 days of injection may be used even if conducted prior to obtaining informed consent if they are ordered and conducted at the direction of the Investigator as part of his/her standard of care.
- d. Timepoint is within 15 minutes post-injection.

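### The only laboratory baseline may be up to 30 days old at injection, so change that precedes tilmanocept can be recorded as post-injection change, and the stated two-week sampling span is not ensured

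*Combined protocol and SAP*

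**What the plan says.** The primary safety objective (Section 2.1) covers adverse events and "changes over time in laboratory tests, vital signs, and physical examination findings".

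Laboratory samples are taken at two visits. Section 7.1 lists "Blood draw for routine hematology and chemistry" and a urinalysis at screening, any day from Day -29 to Day 0. Section 7.2.3 lists the same tests at 5±3 days after injection. Injection is on Day 1. The pre-injection procedures in Section 7.2.1 include no blood draw, and the row "Clinical Laboratory Evaluation" in Appendix 1 is marked only for screening and follow-up. Table 4 in Section 8.3.2 shows 10 mL at each of these two visits, and the text above it gives the total as "approximately 20 mL over a period of approximately 2 weeks".

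Exclusion 4 in Section 4.2 bars chemotherapy, immunotherapy and radiation "within the 10 days prior to Tc 99m Tilmanocept administration". Section 6.1 repeats the 10-day rule. Neither section restricts therapy earlier than that, or between injection and the follow-up draw.

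Section 8.2.1.1 sets the reference for worsening: "Any clinically significant change in condition (worsening) from screening that results in a change in subject management will be considered an AE". Section 8.3.1 requires clinically significant laboratory changes that are not laboratory error to be recorded as adverse events.

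**The concern.** The laboratory panel (hemoglobin, platelets, white cells, creatinine, electrolytes, BUN, ALT, AST) is measured in patients with liver metastases who may be between treatment cycles. Several of these values can move over a month through disease or therapy alone. If the only pre-injection value is weeks old, that movement appears in the difference between screening and follow-up.

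The protocol's own adverse event window makes this matter. Under Section 8.2.1.1, general capture starts on the day of injection, and earlier events count only if related to a trial procedure or the study drug. For laboratory values the rule cannot be applied as intended: with no sample near injection, a fall in platelets before Day 1 looks the same as a fall after it. Such a change, if clinically significant, is recorded as an adverse event. If it is then graded at least possibly related (Section 8.2.1.2), it counts against the primary endpoint, the proportion of subjects without an adverse drug reaction in each dose group.

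Vital signs do not have this problem, because they are measured within 15 minutes before injection.

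**Working it through.** **Inputs**
- Screening draw: Day -29 to Day 0 (Section 7.1).
- Injection: Day 1 (Section 7.2).
- Follow-up draw, reading A: 5±3 days after injection, so Day 3 to Day 9 (Section 7.2.3).
- Follow-up draw, reading B: Day 5±3, so Day 2 to Day 8 (column label in Appendix 1).
- Therapy bar: the last 10 days before injection (Sections 4.2 and 6.1).
- Volumes: 10 mL per draw (Table 4).

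**Figures in the protocol that reproduce**
- Blood volume: 10 + 10 = 20 mL, as stated.
- Time on trial (Section 3.4): 30 days from the earliest screening day to injection, plus the nominal 5 days = 35 days, as stated.

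**Age of the baseline at injection** (injection day minus screening day)
- Shortest: 1 - 0 = 1 day.
- Longest: 1 - (-29) = 30 days.
- Days within the longest interval open to anticancer therapy: 30 - 10 = 20.

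**Span between the two draws** (follow-up day minus screening day)

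| | Minimum | Earliest screening, nominal follow-up | Maximum |
|---|---|---|---|
| Reading A | 3 - 0 = 3 | 6 + 29 = 35 | 9 + 29 = 38 |
| Reading B | 2 - 0 = 2 | 5 + 29 = 34 | 8 + 29 = 37 |

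The stated two weeks (14 days) is neither the maximum nor the nominal full-window span on either reading. It lies inside the permitted range: a 14-day span needs a screening draw between Day -11 and Day -5 (reading A) or Day -12 and Day -6 (reading B), depending on the follow-up day. No section requires this.

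**Illustration only.** The documents do not say when within the windows subjects are seen. If all 30 × 7 = 210 combinations of screening and follow-up day were equally likely, the span would be 14 days or less in 63/210 = 30% (reading A) or 70/210 = 33% (reading B). It would exceed 21 days in 98/210 = 47% or 91/210 = 43%. The mean would be 20.5 or 19.5 days.

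**After the change proposed below**
- Baseline within 10 days before injection, reading A: nominal span at most 10 + 5 = 15 days, maximum 10 + 8 = 18.
- The same on reading B: 10 + 4 = 14 and 10 + 7 = 17.
- Baseline on Day 1 before injection: span 2 to 8 days (A) or 1 to 7 days (B).
- Under either option no day between baseline and injection is open to anticancer therapy.

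**The case against.** The best defence is that attribution in this study rests on case judgement whatever the date of the baseline. The study is open-label, descriptive and has no untreated control. The means for that judgement are provided: all medications from 30 days before injection through follow-up are documented (Section 6.1), factors influencing a laboratory value are recorded with co-medication as a named example (Section 8.3.1), and abnormal values are repeated until they return to baseline or are explained. Causality has five grades, two of them for events better explained by clinical state or other treatment (Section 8.2.1.2). This stands. A reader might infer that laboratory changes cannot be tied to tilmanocept at all, and the documents do not support that. A recent baseline is also permitted, since a Day 0 draw is already allowed. These records help interpret a change, but they do not supply the missing value near injection.

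The route to the primary endpoint is also conditional. A laboratory drift must be clinically significant, alter management, and be judged at least possibly related. One such event would move the reaction-free proportion by 1/6 = 17 percentage points in a cohort of 6, or 1/3 = 33 points among the 3 subjects at a cohort review. Those figures hold for any single event in so small a group and say nothing about how likely misattribution is. Section 9 lists adverse event incidence but no summary of laboratory change, so no planned pre/post laboratory analysis can be shown to be biased.

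Finally, the two weeks in Section 8.3.2 is an approximate remark about blood volume, not an analysis window. It would be wrong to read it as a span that the design fails to deliver, because 14 days is possible. Correcting that phrase alone would be clerical.

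**Conclusion.** The point holds as a weakness in the laboratory baseline that is cheap to correct; it does not invalidate the safety assessment. The baseline may be 1 to 30 days old at injection, with up to about 20 of those days open to anticancer therapy. The two draws may be 3 to 38 days apart (2 to 37 on the Appendix 1 label), so the stated two weeks is not ensured. Because worsening is referred to screening, change before injection can enter the record as a post-injection adverse event, which weakens attribution for a stated part of the primary objective.

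The day counts rest only on the visit windows and on injection falling on Day 1. How often the long intervals would occur, and how far values would drift, cannot be derived from the documents.

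Two limits remain whatever is done about the baseline: therapy is not restricted between injection and follow-up, up to 8 days, and there is no control group.

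**What to change.** Keep two draws and 20 mL, but time the existing baseline hematology, chemistry and urinalysis close to injection. There are two workable options:
- On Day 1 before injection, when a catheter is placed anyway.
- If results are wanted beforehand, within the 10 days before injection, which is the therapy-free window the protocol already has. The nominal span then roughly matches the two weeks in Section 8.3.2. Under the Day 1 option that phrase needs changing.

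Define this sample as the baseline for laboratory change and for laboratory worsening in Sections 8.2.1.1 and 8.3.1. Merely naming the latest pre-injection value as baseline would change nothing while the early screening draw is the only one; it would take a third draw to help.

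Align the synopsis, Sections 7.1, 7.2.1, 8.3.1 and 8.3.2, and Appendix 1. Two related discrepancies should be reconciled at the same time: Section 8.3.1 names only screening for the safety samples, whereas Section 7.2.3, Table 4 and Appendix 1 include follow-up; and the follow-up window in Section 7.2.3 differs by one day from the label in Appendix 1 when injection is Day 1.

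The cost is protocol wording in several places and less freedom in scheduling the screening laboratory visit. With the Day 1 option, results may arrive after injection. Apart from the urine pregnancy test, no entry criterion in Sections 4.1 or 4.2 depends on a laboratory value, so that downside is small, but the sponsor should weigh it when choosing between the two.
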